3 COMPUTED VARIABLES

The following variables will be computed as described below.

In this section, the eCRF fields are indicated as: "label of the field" [*name of the time point / name of the form. name of the eCRF variable*].

In case of partial dates (i.e. day and/or month not known), the Biostatistician will estimate incomplete dates to be used in the statistical analysis as follows: if year is not unknown, missing days will be inputed as the first day of the month (01) and month will be inputed as "July" (07).

Moreover, if a patient is deceased and in the eCRF it is not reported that the patient stopped a specific treatment (ie. the treatment stop date is not provided), then the treatment stop date will be imputed with the date of death.

Number of NSCLC treatment lines and type of lines

For each patient, the total number of NSCLC treatment lines will be calculated as follows:

- If "Number of treatment lines for advanced EGFR-mutated NSCLC within date of data collection" [*PI. PI_num_lines*] = "1", this will correspond also to the total number of lines (this options is applicable only for UNCOMMON MUTATION COHORT). By definition, the line shall be an EGFR-TKI, and the type of treatment will be retrieved in field "Type of EGFR-TKI" [*EAD. EAD_EGFR*].
- If "Number of treatment lines for advanced EGFR-mutated NSCLC within date of data collection" [*PI. PI_num_lines*] = "2", depending on the type of cohort
 - *Uncommon mutation cohort*:
 1. the first-line treatment will be retrieved from the field [*First-line treatment period / TREAT. TREAT_ty*], and in case it is an "EGFR-TKI" the exact therapy will be retrieved from the field "Type of EGFR-TKI" [*EAD. EAD_EGFR*] of the record of the EGFR-TKI ADMINISTRATION DETAILS form having "Start date with this dose (dd/mmm/yyyy)" [*EAD. EAD_start_date*] equal to "Start date of this line (dd/mmm/yyyy)" [*First-line treatment period / TREAT. TREAT_start_date*];
 2. the second-line treatment will be retrieved from the field [*Second-line treatment period / TREAT. TREAT_ty*], and in case it is an "EGFR-TKI" the exact therapy will be retrieved from the field "Type of EGFR-TKI" [*EAD. EAD_EGFR*] of the record of the EGFR-TKI ADMINISTRATION DETAILS form having "Start date with this dose (dd/mmm/yyyy)" [*EAD. EAD_start_date*] equal to "Start date of this line (dd/mmm/yyyy)" [*Second-line treatment period / TREAT. TREAT_start_date*].

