- SUBSEQUENT LINES DETAILS (if applicable, for patients with Number of NSCLC treatment lines (as defined before) >2), considering the concatenation of fields [**SLD**.
SLD_treat (***) , **SLD_treat_sp**, **SLD_radio_YN**]. The start date of this line will correspond to the field [**SLD**.
SLD_start_date], while the stop date of this line (if any) will correspond to the field [**SLD**.
SLD_stop_date]. *The same patient could have more than one record: each record corresponds to a distinct line, which shall be ordered by start date.*

(*) in case it is an "EGFR-TKI", the exact therapy will be retrieved from the field "Type of EGFR-TKI" [**EAD**.
EAD_EGFR] of the record of the EGFR-TKI ADMINISTRATION DETAILS form having "Start date with this dose (dd/mmm/yyyy)" [**EAD**.
EAD_start_date] equal to "Start date of this line (dd/mmm/yyyy)" [*First-line treatment period / TREAT. TREAT_start_date*].

(**) in case it is an "EGFR-TKI" the exact therapy will be retrieved from the field "Type of EGFR-TKI" [**EAD**.
EAD_EGFR] of the record of the EGFR-TKI ADMINISTRATION DETAILS form having "Start date with this dose (dd/mmm/yyyy)" [**EAD**.
EAD_start_date] equal to "Start date of this line (dd/mmm/yyyy)" [*Second-line treatment period / TREAT. TREAT_start_date*].

(***) in case it is an "EGFR-TKI", the exact therapy will be retrieved from the field "Type of EGFR-TKI" [**SLD**.
SLD_EGFR] of the same record.

Having defined the start and end dates of each line, the **Duration of treatment lines** will be calculated as the difference between the stop date of the line (^) and the start date of the line + 1 day.

(^) or the end of observation date (as defined later), in case the therapy line was not discontinued at the end of observation.

*In particular, for each patient, the sequences of treatments will be defined taking into consideration the start dates of each line (as defined before). This way, it will be possible to calculate also the **ordinal number** of each line.* Here below are provided some examples of the treatment line sequence that might be observed:

- EGFR-TKI (afatinib)
- Chemotherapy+Radiotherapy → EGFR-TKI (erlotinib)
- Chemotherapy+Targeted therapy → EGFR-TKI (gefitinib) → Chemotherapy+Immunotherapy
- etc.

Type of NSCLC treatment patterns for SEQUENCING COHORT

Patient's treatment patterns will be defined as follows:

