Only patients with Number of NSCLC treatment lines (as defined before) > 1 and [**MUT2. MUT2_reeval_stop**] = "Yes" will be considered.

Time on treatment with index therapy EGFR-TKI for UNCOMMON MUTATIONS COHORT

The following patients will be considered as having the event “treatment discontinuation”:

- patients with discontinuation of index EGFR-TKI treatment, ie. those with discontinuation defined as “Treatment discontinued?” [EAD. EAD_treat_disc] = “Yes” in the latest record of the EGFR-TKI ADMINISTRATION DETAILS form referred to the index EGFR-TKI treatment (as defined before). For these patients, the time to event will be computed as the difference between the field “Stop date with this dose” [EAD. EAD_stop_date] of the above-mentioned record and the start date of the Index EGFR-TKI therapy (as defined before) + 1 day;
- deceased patients at time of inclusion in the study, ie. those with [PI. PI_pt_class] = “Deceased patient”. For these patients, the time to event will be computed as the difference between the “Date of death” [PI. PI_date_death] and the start date of the Index EGFR-TKI therapy (as defined before) + 1 day.

The same patient could have multiple events, but for the purpose of the analysis only the earliest event will be considered.

Other patients will be considered as censored observations. The following situations might be observed:

- non-deceased patients with evidence of ongoing treatment at end of observation, ie. those with [PI. PI_pt_class] = (“Living patient” OR “Untraceable patient”) and with “Treatment discontinued?” [EAD. EAD_treat_disc] = “No” in the latest record of the EGFR-TKI ADMINISTRATION DETAILS form referred to the index EGFR-TKI treatment (as defined before). For these patients, the time to censoring will be computed as the difference between the end of observation date (as defined later) and the start date of the Index EGFR-TKI therapy (as defined before) + 1 day;

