- for **OS from osimertinib discontinuation**, as the difference between the “Date of death” [PI. PI_date_death] and the Stop date of second-line therapy (as defined before, namely osimertinib) + 1 day. This algorithm will be computed only for patients with osimertinib discontinuation (ie. those with calculated stop date of second-line therapy).

Other patients will be considered as censored observations. The following situations might be observed:

- alive patients at end of observation, ie. those with [PI. PI_pt_class] = “Living patient”. For these patients, the time to censoring will be computed as the difference between the end of observation date (as defined later) and the start date of afatinib / stop date of osimertinib therapy (depending on the type of OS evaluated) + 1 day;
- untraceable patients at end of observation, ie. those with [PI. PI_pt_class] = “Untraceable patient”. For these patients, the time to censoring will be computed as the difference between the latest date when the patient was known to be alive (ie. [PI. PI_date_alive]) and the start date of afatinib / stop date of osimertinib therapy (depending on the type of OS evaluated) + 1 day.

End of observation date

- For alive patients (ie. those with [PI. PI_pt_class] = “Living patient”), it will correspond to the “Date of data collection (dd/mmm/yyyy)” [PI. PI_date_coll]
- For deceased patients (ie. those with [PI. PI_pt_class] = “Deceased patient”) it will correspond to the “Date of death (dd/mmm/yyyy)” [PI. PI_date_death]
- For untraceable patients (ie. those with [PI. PI_pt_class] = “Untraceable patient”) it will correspond to the “Date patient last known to be alive (dd/mmm/yyyy)” [PI. PI_date_alive]

Duration of observation window (in months) starting from the first-line treatment start

- For alive patients (ie. those with [PI. PI_pt_class] = “Living patient”), it will be calculated as the difference between the end of observation date (as defined before) and Start date of first-line therapy (as defined before) + 1 day
- For deceased patients (ie. those with [PI. PI_pt_class] = “Deceased patient”) it will be calculated as the difference between the end of observation date (as defined before) and Start date of first-line therapy (as defined before) + 1 day

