4.2.5 Time on treatment

Table 20-SEQ. Time on treatment (ELIGIBLE PATIENTS of the Sequencing Cohort) – Primary objective

The table will provide the Kaplan-Meier estimates of quartiles of time on treatment with the pattern afatinib-osimertinib (with their 95% Confidence Intervals, using Greenwood's variance estimate) (see "Computed variables" chapter). Moreover, a Kaplan-Meier survival curve will be provided. The analysis will be represented on a plot having the time to event on the horizontal axis and the percentage of event-free patients on the vertical axis.

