4.2.6 Overall Survival

Table 21-SEQ. Overall Survival from afatinib start (ELIGIBLE PATIENTS of the Sequencing Cohort) - Secondary objective #2

The table will provide the Kaplan-Meier estimates of quartiles of time to death from afatinib start (with their 95% Confidence Intervals, using Greenwood's variance estimate) (see algorithm for Overall Survival in the "Computed variables" chapter).

Moreover, a Kaplan-Meier survival curve will be provided. The analysis will be represented on a plot having the time to event on the horizontal axis and the percentage of event-free patients on the vertical axis.

Table 22-SEQ. Overall Survival from osimertinib discontinuation (ELIGIBLE PATIENTS of the Sequencing Cohort)

[figure not shown]
The table will provide the Kaplan-Meier estimates of quartiles of time to death from osimertinib discontinuation (with their 95% Confidence Intervals, using Greenwood's variance estimate) (see algorithm for Overall Survival in the "Computed variables" chapter).

Moreover, a Kaplan-Meier survival curve will be provided. The analysis will be represented on a plot having the time to event on the horizontal axis and the percentage of event-free patients on the vertical axis.

In this analysis, only patients who discontinued osimertinib (see "Computed variables" chapter) will be considered.

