6 QUALITY CHECKS ON THE STATISTICAL REPORT

The statistical analysis of the UPSWING study will be managed by 3 main figures in [REDACTED]: the Biostatistician (BS), the [REDACTED]. In particular, in this context, [REDACTED] of data cleaning, database creation, management and lock, while BS is the owner of Statistical Analysis Plan and Statistical Report redaction.

BS and [REDACTED] of the UPSWING study have performed an annual training of at least 30 hours and an induction training concerning knowledge and skills required for the management of observational studies with a focus on their role. Furthermore they are coordinated by R-DMS who possesses qualifications necessary for her job.

Moreover, regarding instruments, database management and data analysis will be performed using SAS Enterprise Guide v. 7.1 and SAS 9.4.

Actions to improve the quality of data are taken in different moments during the study and using various tools, as described in [REDACTED] Standard Operating Procedures concerning data cleaning and statistical analysis.

Data validation (see Data Validation Plan) foresees both on-line (electronic CRF allows to verify data at the moment they are entered by means of automated edit checks, out of range controls, etc.) and off-line checks. Subsequently, quality control continues at the moment of the database lock when, as requested by [REDACTED] procedure, the [REDACTED] can lock the database only if, among other conditions, BS and Sponsor approve the quality of data (i.e. In defining if the obtained quality of data is sufficient, the impact of possible missing/inconsistent data remained after all possible efforts to fix are done, will be based on the impact of these data on the primary and the secondary study objectives).

Finally, a quality control of the data analysis process focused on the detection of possible calculation errors or inconsistent data is performed. To observe the recommendation about the detection of priorities in order to make the process more efficient, the type of statistical report quality control is defined on the basis of the risk analysis conducted for the study.

The following quality controls will be performed on the statistical report of the UPSWING study.

- All the tables described in this document will be programmed and verified by a BS.

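### Partial dates are set to day 01 or July with no check against recorded dates, so a guessed death can replace a recorded treatment stop and make survival after stopping zero or negative

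*SAP*

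**What the plan says.** SAP section 3 (Computed variables) opens with a general rule: "In case of partial dates (i.e. day and/or month not known), the Biostatistician will estimate incomplete dates". It then states that "missing days will be inputed as the first day of the month (01) and month will be inputed as" July, provided the year is known. No type of date is exempt, and no other date limits the result. A second rule sets the treatment stop to the date of death, but only for a deceased patient with no stop date.

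The same section builds the endpoints from these dates:

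- **Time on treatment (both cohorts, primary) and time to second-line failure (uncommon mutation cohort, secondary).** Discontinuation and death are both events: "The same patient could have multiple events, but for the purpose of the analysis only the earliest event will be considered".
- **Overall survival from osimertinib discontinuation (sequencing cohort, Table 22-SEQ).** This is death minus stop plus 1 day, with no floor. The only entry condition is a calculated stop date.
- **Duration of treatment lines.** This is "the difference between the stop date of the line (^) and the start date of the line + 1 day", or the end of observation if the line is ongoing.

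The SAP's only case-by-case provision for an unknown day concerns the 11.50-month and 9.50-month eligibility windows in section 2.1.

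**The concern.** The rule can place an imputed date on the wrong side of a recorded one. There are three consequences.

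1. An imputed death that falls before a recorded stop becomes the earliest event, so a known date is replaced by a guess. The event status does not change, but the time is shortened.
2. Survival from discontinuation can be zero or negative. The SAP does not say whether such values are dropped, set to a minimum or corrected, so the choice would be made after the outcomes are seen. When a partial death date causes the problem, these patients truly died soon after stopping: within about 6 months if only the year is known, within a month if only the day is missing. Dropping them lengthens the survival estimate.
3. A line duration can be negative.

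Partial dates are to be expected here. The study is a retrospective chart review, the protocol (9.2, 9.2.1) asks for deceased patients wherever possible, and protocol 9.9 anticipates missing or inconsistent data.

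**Working it through.** The plan states no figure on this point, so the check applies its rules to dates and then sizes the effect under stated assumptions.

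**Formulas.** Time on treatment = min(stop, death) - start + 1 day. Survival after stopping = death - stop + 1 day. Months = days / 30.4375, the divisor the SAP uses for disease duration.

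**Death imputed, stop recorded** (afatinib start 10 January 2017)

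- Stop 10 October 2019, death known as 2019, imputed to 1 July 2019. Time on treatment is 903 days (29.67 months) instead of 1,004 days (32.99 months). Survival after stopping is -101 + 1 = -100 days.
- Stop 20 October 2019, death known as October 2019, imputed to 1 October. Time on treatment is 995 days (32.69 months) instead of 1,014 days (33.31 months). Survival after stopping is -19 + 1 = -18 days.

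**Stop imputed**

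- Stop known as 2019, imputed to 1 July; death recorded on 10 March 2019: -113 + 1 = -112 days.
- Stop known as 2019; death known as March 2019, imputed to 1 March: -122 + 1 = -121 days.
- Line started 10 March and stopped in March of the same year, day unknown: duration -9 + 1 = -8 days.

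**How often, given a partial death date.** With a year-only death in the year of the stop, 183 of 365 possible stop dates give a survival of zero or less (minimum -182 days). With only the day missing and a stop in the same 31-day month, 30 of 31 stop days do (minimum -29 days). Assume an exponential gap from stop to death and deaths spread evenly over the year:

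| Median gap (months) | Year-only death: imputed death before stop | Day missing: imputed death before stop |
|---|---|---|
| 1 | 38% | 27% |
| 3 | 23% | 10% |
| 6 | 14% | 5% |
| 12 | 8% | 3% |

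An affected patient loses on average 2.1 to 2.5 months (year-only) or about 11 days (day missing) of time on treatment.

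**Effect on the reported medians.** The simulation uses 4,000 cohorts of 200 patients, an exponential time on treatment with the protocol's 30-month median (9.5), and 10% random censoring. For Table 22-SEQ it adds 30% censoring. Shares of year-only deaths among stopped patients are assumed. Shifts are means in months against the median from the true dates: earlier for the primary endpoint, later for Table 22-SEQ.

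| Year-only share | Median gap (months) | Patients affected | Primary median unchanged | Primary shift | Table 22-SEQ shift, non-positive times excluded | Table 22-SEQ shift, imputation bounded |
|---|---|---|---|---|---|---|
| 1% | 6 | 0.25 | 99.2% | 0.004 | 0.025 | 0.013 |
| 1% | 12 | 0.15 | 99.6% | 0.002 | 0.025 | 0.007 |
| 5% | 3 | 2.06 | 94.3% | 0.023 | 0.131 | 0.070 |
| 10% | 1 | 6.90 | 80.2% | 0.080 | 0.136 | 0.060 |
| 10% | 3 | 4.21 | 88.9% | 0.041 | 0.261 | 0.134 |
| 10% | 12 | 1.39 | 95.9% | 0.017 | 0.206 | 0.051 |

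The largest count follows directly: 180 stopped patients x 10% x 0.384 = 6.9.

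**Yardstick.** Protocol Table 9.5:1 gives an expected confidence interval width of 13.7 months at 10% censoring. A simulation with exponential times gave 12.1 to 12.2 months, so that figure was not reproduced exactly. Against either width, a shift of 0.08 months is negligible.

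**The case against.** The strongest reply is that very little moves. The effect on the primary median is negligible, event status is unchanged, the study makes no comparison, and Table 22-SEQ is not tied to a numbered objective. All of that stands, and it limits the weight of the point.

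The upper count can also be challenged, because the year-only share was applied to stopped patients rather than to deaths. The earlier real-world study of this sequence had 31% survival maturity (protocol 7.2). Taking that as an illustration, 31% of 200 is 62 deaths, and 62 x 10% x 0.384 = 2.4 patients at most. The protocol expects higher maturity this time, so 2.4 is on the low side. It lies within the range given.

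When the stop is partial and the death recorded, the earliest-event rule uses the recorded death, so that case does not shorten the primary endpoint. This is correct.

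On detection, SAP section 6 says that "a quality control of the data analysis process focused on the detection of possible calculation errors or inconsistent data is performed", and adds a plausibility review and a 100% re-check of the primary tables. A sequencing patient with -100 days in Table 22-SEQ may well be noticed, although that table's algorithm is checked in only 20% of patients. In the visible text the uncommon mutation cohort has no such table, and its shortened time looks plausible and agrees with the specification, so reprogramming would reproduce it. Entry checks do not help: a stop of 10 October 2019 and a death in 2019 are consistent until the imputation is made. The Data Validation Plan is not available and may prompt queries. Even so, the SAP gives no rule for dates that stay partial, nor for a non-positive time once found.

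**Conclusion.** The concern holds. Followed as written, the SAP replaces recorded stop dates with guessed deaths and produces impossible survival times and line durations. This is an error in the stated rule, not a missing detail.

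Its size is small. Under the assumed shares of 1% to 10%, about 0.15 to 6.9 patients are affected, and the primary median moves by 0.002 to 0.08 months on average. Table 22-SEQ is the most exposed: excluding the non-positive times moves its median 0.02 to 0.26 months later. The date examples need no assumptions. The rates do, because the documents give neither the share of partial dates nor the gap from stop to death. The rule should be corrected because the defect is certain and the remedy is cheap. The primary result is not in danger.

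**What to change.** Keep the day 01 and July default and add to SAP section 3:

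- An imputed date must lie within the interval allowed by its own known parts and by the recorded parts of adjacent dates, in the order start <= stop <= death, last known alive or data collection. If the default falls outside, use the nearest admissible date.
- An imputed date never overrides a complete recorded date.
- If two adjacent dates are both partial, limit each by the known parts of both. Impute the one with more known parts first (the earlier event if equal) and use it as the bound for the other. Raise a query only if no ordered pair is possible. A stop in 2019 with a death in March 2019 then gives 1 March 2019 for both.

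On 400,000 random sets of start, stop and death dates with up to two missing parts, this rule gave no ordering violations, changed no complete date and raised no needless query.

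The drawback is that a death moved to the bound receives the minimum survival of 1 day after stopping. In the first example the true value could be anything from 1 to 83 days (10 October to 31 December). A footnote to Table 22-SEQ should therefore report how many patients were handled this way. Querying the site before imputing, or using the midpoint of the admissible interval, would be compatible refinements.

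The cost is a few sentences of SAP text, one programmed ordering check and one footnote count.

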- by definition, "Afatinib" will be the first-line treatment; the start date of the line will be the earliest start date of the field [AAD. AAD_start_date], while the stop date of the line will be the greatest stop date of the field [AAD. AAD_stop_date];
- by definition, "Osimertinib" will be the second-line treatment; the start date of the line will be the earliest start date of the field [OAD. OAD_start_date], while the stop date of the line will be the greatest stop date of the field [OAD. OAD_stop_date];
- subsequent lines will be defined according to the data recorded in the following forms SUBSEQUENT LINES DETAILS (if applicable, for patients with Number of NSCLC treatment lines (as defined before) >2), considering the concatenation of fields [SLD. SLD_treat (**), SLD_treat_sp, SLD_radio_YN]. The start date of this line will correspond to the field [SLD. SLD_start_date]. *The same patient could have more than one record: each record corresponds to a distinct line, which shall be ordered by start date.*

(***) in case it is an "EGFR-TKI", the exact therapy will be retrieved from the field "Type of EGFR-TKI" [SLD. SLD_EGFR] of the same record.

Having defined the start and end dates of each line, the **Duration of treatment lines** will be calculated as the difference between the stop date of the line (^) and the start date of the line + 1 day.

(^) or the end of observation date (as defined later), in case the therapy line was not discontinued at the end of observation.

*In particular, for each patient, the sequences of treatments will be defined taking into consideration the start dates of each line (as defined before). This way, it will be possible to calculate also the **ordinal number** of each line.*

EGFR-TKI generation

- "Erlotinib" and "Gefitinib" will be classified as "1st generation EGFR-TKI";
- "Afatinib" will be classified as "2nd generation EGFR-TKI";
- "Osimertinib" will be classified as "3rd generation EGFR-TKI".

EGFR-TKI starting daily dose (mg) (first- and second-line treatment only)

The starting dose will be retrieved from the following fields of the following forms:

- from the AFATINIB ADMINISTRATION DETAILS form (only for the SEQUENCING COHORT), from the field [AAD. AAD_dose] of the record with earliest non-missing start date (recorded in field [AAD. AAD_start_date]);

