- non-deceased patients with unknown information on treatment interruption at end of observation, ie. those with [PI. PI_pt_class] = (“Living patient” OR “Untraceable patient”) and with “Treatment discontinued?” [EAD. EAD_treat_disc] = “UNK” in the latest record of the EGFR-TKI ADMINISTRATION DETAILS form referred to the index EGFR-TKI treatment (as defined before). For these patients, the time to censoring will be computed as the difference between the greatest start date [EAD. EAD_start_date] of the EGFR-TKI ADMINISTRATION DETAILS form referred to the index EGFR-TKI treatment (as defined before) and the start date of the Index EGFR-TKI therapy (as defined before) + 1 day.

Time on treatment for SEQUENCING COHORT

The following patients will be considered as having the event “osimertinib treatment discontinuation after switch from afatinib”:

- patients with discontinuation of osimertinib treatment, ie. those with discontinuation defined as “Treatment discontinued?” [OAD. OAD_treat_disc] = “Yes” in the latest record of the OSIMERTINIB ADMINISTRATION DETAILS form. For these patients, the time to event will be computed as the difference between the field “Stop date with this dose” [OAD. OAD_stop_date] of the above-mentioned record and the start date of the first-line therapy (as defined before) + 1 day;
- deceased patients at time of inclusion in the study, ie. those with [PI. PI_pt_class] = “Deceased patient”. For these patients, the time to event will be computed as the difference between the “Date of death” [PI. PI_date_death] and the start date of the first-line therapy (as defined before) + 1 day.

The same patient could have multiple events, but for the purpose of the analysis only the earliest event will be considered.

Other patients will be considered as censored observations. The following situations might be observed:

- non-deceased patients with evidence of ongoing treatment at end of observation, ie. those with [PI. PI_pt_class] = (“Living patient” OR “Untraceable patient”) and with “Treatment discontinued?” [OAD. OAD_treat_disc] = “No” in the latest record of the OSIMERTINIB ADMINISTRATION DETAILS form. For these patients, the time to censoring will be computed as the difference between the end of observation date (as defined later) and the start date of the first-line therapy (as defined before) + 1 day;

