4 CONTENTS

The analyses will be performed on the Analysis set specified for each table.

Missing data will not be imputed and so patients with missing data will be excluded from the analyses of that variable(s).

If the investigator is unable to collect the requested information the data will be “NK” (Not Known) or “NA” (Not Available), if the investigator did not record the information the data will be “Not Recorded”.

The UPSWING study has descriptive objectives and no specific comparison will be performed. The estimation of confidence intervals limits will be performed, where relevant.

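### Table 22-SEQ (survival after osimertinib discontinuation) counts a deceased patient with no recorded osimertinib stop date as a death at 1 day

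*SAP*

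**What the plan says.** Four statements in the SAP determine who enters Table 22-SEQ and with what survival time.

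- **Missing stop dates.** The opening of Chapter 3 says that if a patient has died and no stop date was given for a treatment, "then the treatment stop date will be imputed with the date of death".
- **Stop date of the osimertinib line.** In the treatment-pattern rules for the sequencing cohort, "the stop date of the line will be the greatest stop date of the field [OAD. OAD_stop_date".
- **Survival time and entry rule.** Overall survival from osimertinib discontinuation is the date of death minus the stop date of second-line therapy, plus 1 day. The entry rule reads: "This algorithm will be computed only for patients with osimertinib discontinuation (ie. those with calculated stop date of second-line therapy".
- **The table itself.** Section 4.2.6 says: "In this analysis, only patients who discontinued osimertinib" are considered. It refers to the computed-variables chapter for what that means, and asks for Kaplan-Meier quartiles with 95% confidence intervals and a curve.

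**The concern.** Table 22-SEQ is meant to describe how long patients live after stopping osimertinib. A patient who died while still taking it has no survival after discontinuation to describe. A patient who stopped earlier on an unrecorded date has such a survival time, but it is unknown. The death-date rule gives both the shortest possible value, 1 day, and counts it as an event.

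The rule is also one-sided. A living or untraceable patient with no stop date gets no imputed date and is left out, so missing stop dates add deaths and never censored observations.

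Such patients are plausible here. Protocol 9.2 and 9.2.1 ask for deceased patients to be enrolled whenever possible, 9.9 warns of missing data in retrospective collection, and the SAP wrote a rule for exactly this situation.

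**Working it through.** **Step 1: the time assigned.** With stop date set equal to date of death, time = death − death + 1 = 1 day, or 1/30.4375 = 0.033 months, counted as a death. A partial death date gives the same result, because the stop date copies it.

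**Step 2: does anything remove these patients?**
- Eligibility (SAP 2.1, criterion 6 for the sequencing cohort) requires osimertinib start dates, not stop dates.
- SAP 2.3 requires data for the primary analysis. A deceased patient has a primary event at death and so qualifies.
- Section 4.2.6 restricts the table to patients who discontinued, but takes the definition from Chapter 3, where an imputed stop date is a calculated one.

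They stay in.

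**Step 3: effect on the quartiles.** The plan gives no figure to reproduce and no count of affected patients, so this is an illustration. Let a share q of the table be 1-day entries (assumed), and let S0(t) be the survival curve of the rest. All 1-day deaths precede any later censoring, so after day 1 the Kaplan-Meier curve estimates S(t) = (1 − q) × S0(t).

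With exponential S0, solving S(t) = 0.75, 0.50 and 0.25 gives these ratios of reported to true quartile, whatever the true median is:
- 25th percentile: ln((1 − q)/0.75) / ln(1/0.75)
- median: ln(2(1 − q)) / ln 2
- 75th percentile: ln((1 − q)/0.25) / ln 4

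| q (assumed) | 25th percentile | Median | 75th percentile |
|---|---|---|---|
| 2% | 0.930 | 0.971 | 0.985 |
| 5% | 0.822 | 0.926 | 0.963 |
| 10% | 0.634 | 0.848 | 0.924 |

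At 5%, for example, the 25th-percentile ratio is ln(1.2667)/ln(1.3333) = 0.2364/0.2877 = 0.822, and the median ratio is ln(1.90)/ln 2 = 0.6419/0.6931 = 0.926.

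**Step 4: sensitivity to shape.** For Weibull survival with shape k, each ratio is raised to the power 1/k. At q = 5%, k = 0.8 gives 0.782 (25th percentile) and 0.908 (median); k = 1.2 gives 0.849 and 0.938.

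**Step 5: in months.** With an assumed true median of 10 months, the true 25th percentile is 10 × ln(1/0.75)/ln 2 = 4.15. At q = 5% the table would read 9.26 (median) and 3.41 (25th percentile); at 10%, 8.48 and 2.63.

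**Step 6: check with censoring.** A simulation with 130 patients, the same 10-month median and about 30% censoring of the true discontinuers gave a median of 9.97 at q = 0 and 8.53 at q = 10%. Later censoring does not change the picture.

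**The case against.** **The SAP treats death as discontinuation elsewhere.** The time-on-treatment rule for the sequencing cohort has two limbs: "patients with discontinuation of osimertinib treatment, ie. those with discontinuation defined as" a Yes in the latest osimertinib record, and deceased patients at their date of death. The duration rule uses the end of observation "in case the therapy line was not discontinued at the end of observation", and for a deceased patient that is also the date of death. A reader might infer that Table 22-SEQ departs from the SAP's own idea of discontinuation; the text does not support that. What remains is that death suits time on treatment as an end point but cannot serve as the time origin for survival after stopping.

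**Section 4 forbids imputation.** It says: "Missing data will not be imputed and so patients with missing data will be excluded from the analyses of that variable(s". A reader might see a contradiction that removes these patients. Chapter 3 has an explicit rule for this date, and the specific rule governs. Listing it as an exception is editorial.

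**Dose changes could act the other way.** The stop-date field is labelled "Stop date with this dose", so a reader might infer that patients still on osimertinib after a dose change also enter, which would leave the net direction unknown. That requires the words in parentheses to override the plain restriction to patients with osimertinib discontinuation, and depends on how the eCRF is filled in, which the documents do not show. It is secondary and conditional.

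**Checks exist.** SAP Chapter 6 has the table recalculated for 20% of patients by the same algorithm, which would reproduce the 1-day times. It also plans a plausibility review, and a large group of 1-day deaths would show as an early drop on the curve. It cannot be said that the checks would miss the problem.

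**Materiality is limited.** The table carries no secondary-objective label, the visible text of Protocol 9.3.2 does not name this time origin, the study is descriptive, and the number affected could be zero. All of this stands.

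**Conclusion.** The point holds. Read together, the death-date rule and the entry rule put every eligible deceased patient without a recorded osimertinib stop date into Table 22-SEQ as a death at 1 day. The effect of the imputation is downward and largest at the 25th percentile. Its size depends on an unknown share: about 7% on the median and 18% on the 25th percentile if that share is 5%, and 15% and 37% if it is 10%, assuming exponential survival in the rest.

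A reader might infer that the primary result or the main survival result is also biased. It is not. In Table 20-SEQ death is itself an event on the same date, so the imputed stop date changes nothing. Table 21-SEQ runs from afatinib start and uses no stop date. This is a definitional error in one supporting survival table, worth correcting because the correction is cheap.

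**What to change.** 1. **Entry rule (SAP Chapter 3, OS from osimertinib discontinuation).** Replace the reference to a calculated stop date with: *patients whose latest osimertinib administration record has* `OAD_treat_disc` *= Yes and a recorded stop date in that record; stop dates imputed with the date of death under Chapter 3 do not qualify.* Section 4.2.6 can stay, since it points here. The same wording settles the dose-change question.
2. **Partial dates.** Do not require the stop date to be strictly before death when either date is partial. Chapter 3 sets an unknown day to the 1st, so a patient who stopped on 10 March and died on an unknown later day in March gets a death date of 1 March and a time of 1 − 10 + 1 = −8 days. Dropping such patients would remove genuine discontinuers who died early and bias survival upward. Keep them; where the partial-date rule puts death on or before the recorded stop date, set the time to 1 day and flag the patient. Where both dates are complete and equal, count the patient as a death on osimertinib.
3. **Counts beside Table 22-SEQ.** Report the number of deaths on osimertinib and the number of patients with an unknown stop date.
4. **Editorial.** In Chapter 4, name the Chapter 3 date rules as exceptions to the no-imputation sentence.

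The cost is a few sentences and two counts. The fields already exist, and the time-on-treatment rule already uses the discontinuation test. The downside is a few fewer patients in Table 22-SEQ. The primary event rules do not change.
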